4.2 Outcome

Improvement of lactate/pyruvate ratio <25 (by different treatment strategies).

5 STUDY DESIGN and METHODS of DATA COLLECTION AND DATA ANALYSIS

Multimodality monitoring parameters that will be included:

Directed management in brain injury.

a) Standard monitoring

Intracranial pressure

Cerebral perfusion pressure (mean arterial pressure – intracranial pressure)

Brain tissue oxygen tension

Pressure reactivity index (PRx)

Therapy intensity levels

b) Microdialysis parameters

Metabolic intermediaries (lactate, pyruvate, glucose, glutamate, glycerol)

Cytokine analysis

Nitric oxide

c) CSF parameters

Cytokines and chemokines

d) Serum

Circulating cytokines, chemokines, tissue damage markers (S100B)

The monitoring data will be stored automatically. The chemokine, cytokine and tissue damage marker samples will be analysed using commercially available LUMINEX kits by members of the research team.

Standardized questionnaires to assess extended Glasgow Outcome Score (eGOS) as well and Short Form 36 (SF-36) will be used during the follow-up appointment in the outpatient clinic by members of the research team.

Data will be analysed by members of the research team using comparative statistics between patients with different pathological targets. The statistical program R will be used.

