Study Co-ordinator	[name] [name], MD, PhD. Mail: Division of Neurosurgery, [name] [contact] E-mail: [contact] [contact]
Sponsor	[name], R&D Manager Mail: Cambridge University Hospitals NHS Foundation Trust, [name] [contact] E-mail: [contact] [contact]
Joint-sponsor(s)/co-sponsor(s)	University of Cambridge, Cambridge, United Kingdom
Funder(s)	Swedish Society of Medicine
Key Protocol Contributors	N/A
Committees	N/A

Directed management in brain injury.

STUDY SUMMARY

Study Title	Multimodality Monitoring Directed Management of Patients Suffering from Traumatic Brain Injury
Internal ref. no. (or short title)	Directed management in brain injury
Study Design	Controlled trial without randomisation
Study Participants	Patients with traumatic brain injury and need for intracranial monitoring.
Planned Size of Sample (if applicable)	100
Follow up duration (if applicable)	6 months
Planned Study Period	5 years
Research Question/Aim(s)	
Primary aim:
 
Establish and validate a clinical protocol for microdialysis derived chemistry driven therapy in TBI and see if it improves lactate:pyruvate ratio (<25).
 
Secondary aims:
 
Determine the optimal strategies for correcting abnormalities in microdialysis derived parameters.
 
Determine the inflammatory, tissue and functional outcome for patients suffering from different defined pathological conditions

Directed management in brain injury.

FUNDING AND SUPPORT IN KIND

FUNDER(S) (Names and contact details of ALL organisations providing funding and/or support in kind for this study)	FINANCIAL AND NON FINANCIAL SUPPORT GIVEN
Swedish Society of Medicine	214.000 SEK (Swedish Krona ~ 20.000£)

Directed management in brain injury.

ROLE OF STUDY SPONSOR AND FUNDER

The study sponsor will guarantee that the study will be performed according to rules and regulations, and will assume overall responsibility for the initiation and management of the study.

The Funder will guarantee salary for [name]. The funder will have no role in study design, conduct, data analysis and interpretation, manuscript writing, and dissemination of results.

Neither sponsors nor funder will have control over the final decision regarding any of these aspects of the study.

Directed management in brain injury.

ROLES AND RESPONSIBILITIES OF STUDY MANAGEMENT COMMITTEES/GROUPS & INDIVIDUALS

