3 THEORETICAL FRAMEWORK

We aim to include all traumatic brain injured patients admitted to the neuro-critical care unit that are being monitored and have multi-modality monitoring already in place. As all patients will follow the same protocol, we will minimize the risk of selection and researcher bias. As the patient will be unconscious during this process, next of kin will be asked for consent. As mentioned, this is a structured form of the standard treatments already provided in intensive care.

We will specifically identify patients in whom the microdialysis lactate:pyruvate ratio (LPR) increase above 25. This threshold has been proven to relate to a worse outcome after head injury. This will trigger our protocol which will consist of the following steps:

1. If ICP >20 mmHg, we will aim to escalate intracranial pressure decreasing measures by administering hypertonic saline (5%) 100 ml and if necessary continue on with further ICP decreasing measures.
2. If the brain oxygen pressure falls <15 mmHg, and the pressure reactivity index is >0.3 (an indication that the normal auto-regulation of the brain blood flow is not functioning properly), will increase the cerebral perfusion pressure by 10-20 mmHg.
3. If this still does not improve the brain oxygen pressure, we will increase the flow of inspired oxygen up to a maximum of 60-80%.
4. These steps do not adjust the LPR and if there is a decrease in glucose in the affected brain tissue (<1 mmol/l), we will increase the plasma glucose levels to a maximum 10 mmol/l in order to ensure that the correct amount of nutrients is being delivered, using 50% dextrose (sugar) solution.
5. If all the above steps fail to improve the LPR, it could be due to mitochondrial failure, the powerhouse of the cell. There are currently no approved therapies for this condition. However, at the treating physicians discretion, energy supplementation (e.g. succinate) or neuro-protective drugs (e.g. cyclosporine A) could be provided.

Directed management in brain injury.

Following a 6 month period, we will see the patients in our outpatient clinic to assess functional outcome. This is part of the patient's standard clinical care as all our patients are offered clinical follow up in this way.

We will collect any biological samples that are available as part of the standard clinical care of the patient and will not subject the patients to any additional procedures. This would consist of:

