4.1 Objectives

1. We wish to determine which of the provided therapies that was superior to others in improving the deranged brain metabolism.
2. We also wish to determine the inter-relationships between parameters detected using the microdialysis and other monitoring techniques, such as brain oxygen saturation and perfusion pressure in the damaged brain, and how microdialysis may complement these techniques.
3. How the protocol will alter cytokine, chemokine and markers of brain damage markers (S100B) in serum and microdialysate for patients suffering from different pathological states?
4. How will the functional outcome distribution be for patients suffering from different pathological states?

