7.3 Recruitment

Members of the research team will daily approach the staff in the neuro-critical care unit to determine if any of the newly admitted patients are eligible for inclusion in the study.

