8.1 Assessment and management of risk

The study is designed to closely follow the standard clinical management of traumatic brain injury. Patients with injuries severe enough to participate in this study are by definition unconscious, and will not suffer any discomfort from the study. We will work closely with the treating clinicians and ensure that they are happy with every aspect of the protocol in each individual patient and that the opinion of the treating clinician is respected.

As this protocol is a more structured version of the conventional therapy provided on a regular basis, we do not believe that there will be any additional risks with this protocol.

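### Section 5 gives the 6-month eGOS to the research team and does not mask assessors to pathological state, so the between-state comparison in objective 4 is open to assessment bias

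*Protocol*

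**What the plan says.** Functional outcome by pathological condition is a secondary aim (section 4) and becomes objective 4 in section 4.1: "How will the functional outcome distribution be for patients suffering from different pathological states". Section 5 names the instruments, beginning "Standardized questionnaires to assess extended Glasgow Outcome Score (eGOS" and adding SF-36, and says that they "will be used during the follow-up appointment in the outpatient clinic by members of the research team". Appendix 2 lists the 6-month contact as a follow-up interview.

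The same collective appears elsewhere. Section 7.3: "Members of the research team will daily approach the staff in the neuro-critical care unit". Section 8.1, speaking for the study team: "We will work closely with the treating clinicians and ensure that they are happy with every aspect of the protocol in each individual patient". Section 5 on analysis: "Data will be analysed by members of the research team using comparative statistics between patients with different pathological targets".

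The one stated protection against researcher bias is in section 3: "As all patients will follow the same protocol, we will minimize the risk of selection and researcher bias". The study summary gives the design as "Controlled trial without randomisation".

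**The concern.** Grading an eGOS interview involves some judgement, particularly between adjacent categories. If the assessor knows which pathological state the patient was assigned to, expectation can influence borderline grades. Because objective 4 compares those same states, any grading shift that differs by state would look like a real difference in outcome. No later analysis can separate the two.

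This is a matter of study conduct, settled when the 6-month visits are organised. The protocol already says who takes the assessments, and a statistical analysis plan would not normally repair that choice. At stake is the credibility of a stated secondary aim, not the primary result.

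**Working it through.** The protocol states no figure for assessment error or bias, so there is nothing to reproduce. The check sets the relevant sections side by side.

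1. **Who assesses.** Section 5: members of the research team, at the outpatient follow-up.
2. **What else that team does.** It screens daily with unit staff (sections 7.3 and 7.3.1), runs the biomarker assays and analyses the data (section 5), looks after the database (section 8.7), and alone has access to the final dataset (section 8.10, study team). Section 8.1 puts the study team in contact with the treating clinicians over each patient. Appendix 2 lists observation of treatment and monitoring but does not say who carries them out.
3. **What separates assessors from that knowledge.** Nothing stated. The protocol mentions no blinding, independent assessor, central scoring, or locking of scores before linkage.
4. **Whether the section 3 safeguard covers it.** It does not. A common treatment protocol standardises how patients are managed. It has no bearing on how an interviewer grades outcome six months later.
5. **Which comparison is exposed.** Objective 4 is by pathological state, and section 5 plans comparisons between patients with different pathological targets. Knowledge of state is therefore the relevant threat.
6. **Which outcomes are exposed.**
   - The lactate/pyruvate ratio, the only outcome named in section 4.2, is not. It comes from microdialysis during intensive care, and section 5 says that monitoring data are stored automatically.
   - SF-36 is the patient's own report, so it is less exposed.
   - The eGOS carries most of the risk.

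**Size.** It cannot be derived. The protocol gives n = 100 but not the number or size of the groups, the share reaching follow-up, an eGOS cut, or expected rates.

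The following is purely illustrative of how sensitive small groups are. It assumes a favourable/unfavourable cut that the protocol does not state, and re-grading all in one direction within one state. If k of m patients in a state cross the cut, that state's proportion moves by k/m:

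| Assumed m | k = 2 | k = 3 |
|---|---|---|
| 20 | 2/20 = 10 points | 3/20 = 15 points |
| 25 (100/4) | 2/25 = 8 points | 3/25 = 12 points |
| 33 (about 100/3) | 2/33 ≈ 6 points | 3/33 ≈ 9 points |

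Both k and m are invented inputs. The table does not estimate bias in this trial, and the conclusion does not rest on it.

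**The case against.** The strongest reply is that the protocol refers to members of a team, not to the same individuals. Recruiters, bedside observers and interviewers could be different people, and the assessor might never have seen the monitoring data. This stands. A reader might infer that outcome will in fact be graded by people who know each patient's state, but the text only permits that and does nothing to prevent it.

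Second, a reader might infer that knowledge of the lactate/pyruvate response is the problem, with non-responders expected to do badly. No objective compares functional outcome by that response. Step 5 in section 3 hints at a group defined by failure to respond, but does not define it as a state.

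Third, a reader might infer that the team holds a written expectation about which states do worse. Section 3 ties a ratio above 25 to worse outcome, but the study flow chart makes that the entry condition for every included patient, so it does not rank the states. Objective 4 is put as an open question.

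Fourth, standardized questionnaires narrow the assessor's discretion. They reduce the risk for eGOS without removing it.

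Fifth, the aim is secondary and the study is not randomised, so confounding between states remains whoever grades. That limits the importance of the point. It is not a reason to leave in a source of bias that can be reduced cheaply.

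**Conclusion.** The point holds in a limited form. Section 5 assigns the eGOS to a team that also screens, works with the treating clinicians and analyses the data, and the protocol does not mask assessors to pathological state. The eGOS may therefore be graded with knowledge of state, and the between-state comparison in objective 4 could be biased. Neither the direction nor the size of any bias can be stated from the protocol.

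The conclusion rests on two assumptions: that some discretion remains in eGOS grading despite the standardized questionnaire, and that a team member taking the assessment could know or look up the patient's state. The protocol does not support saying that unmasked grading will occur, that the primary outcome is compromised, or that SF-36 is equally affected. This is an inexpensive improvement to a secondary aim.

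**What to change.** Add a paragraph to section 5 stating that:

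- the eGOS is taken, or scored from the completed standardized questionnaire, by an existing team member who was not involved in that patient's recruitment or bedside management and who, where feasible, has no access to the monitoring data or state label;
- scores are entered and locked before they are linked to the monitoring data;
- the form records whether the assessor was aware of the patient's state and, where so, results for objective 4 are shown with and without those assessments.

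Locking before linkage and recording awareness can be done even where masking fails. The cost is the paragraph, some rota planning and occasional rescheduling. The protocol does not give the team's size, and follow-up is part of routine care at a single centre, so full masking may not always be achievable. Scoring from the completed questionnaire is the fallback when the clinic interviewer already knows the patient. No treatment step changes.

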8. ETHICAL AND REGULATORY COMPLIANCE	
9. DISSEMINATION POLICY	
10. REFERENCES	
11. APPENDICES	

Directed management in brain injury.

STUDY FLOW CHART

If a patient presents with a L/P ratio >25 we will include the patient in the study. As the different monitoring thresholds are reached, it will trigger different treatment strategies in order to treat a specific pathological substrate.

Excess serum, CSF and microdialysis samples will be stored for analyses of inflammatory markers and tissue damage markers.

Follow-up at 6 months following trauma will be done through outpatient clinic.

Directed management in brain injury.

STUDY PROTOCOL

Multimodality Monitoring Directed Management of Patients Suffering from Traumatic Brain Injury

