7.1.2 Exclusion criteria

- a) Bilateral fixed and dilated pupils
- b) Bleeding diathesis
- c) Thrombocytopenia (platelets < 100)
- d) Devastating injuries; patient not expected to survive > 24 hours
- e) Brainstem damage
- f) Pregnancy
- g) Involvement in other studies non-observational studies
- h) MD catheter located in haemorrhagic lesion

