11.2 Appendix 2 – Schedule of Procedures

Procedures	Visits (insert visit numbers as appropriate)				
	Screening	Baseline	Week 1-2	6 Months	
Informed consent	x				
Demographics		x			
Medical history		x			
Observation of treatment		x	x		
Monitoring			x		
Follow-up interview				x	

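### The 6-month eGOS and SF-36 have a clinic appointment as their only stated route, so living patients who do not attend have no score and functional outcome by pathological state may look better than it is

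*Protocol*

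**What the plan says.** Three places in the Protocol describe the 6-month assessment, and all three name the clinic.

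- Study Flow Chart: "Follow-up at 6 months following trauma will be done through outpatient clinic".
- Section 3 (Theoretical Framework): "we will see the patients in our outpatient clinic to assess functional outcome". It adds that this is standard care and that "all our patients are offered clinical follow up in this way".
- Section 5 (Study Design and Methods): the eGOS and SF-36 questionnaires "will be used during the follow-up appointment in the outpatient clinic by members of the research team".

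Appendix 2 (Schedule of Procedures) lists one 6-month item, "Follow-up interview", without stating mode or respondent. No section gives a telephone, postal, home or carer route, or says how vital status at 6 months is established.

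The data serve section 4.1, Objective 4: "How will the functional outcome distribution be for patients suffering from different pathological states". The outcome in section 4.2 is a lactate/pyruvate ratio below 25 and does not depend on this visit.

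**The concern.** Objective 4 asks for a whole distribution, split by pathological state. Being too disabled to travel, or still living in an institution, is part of the outcome being measured. A collection rule that depends on coming to a clinic therefore puts the lower part of the scale among survivors at most risk of being missing.

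Severe outcomes will occur in this cohort. Patients are unconscious and need intracranial monitoring, and the relevant exclusion in section 7.1.2 removes only "Devastating injuries; patient not expected to survive > 24 hours".

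Where and how a score is collected belongs in a protocol. An analysis plan can define how missing scores are handled, but it cannot recover the score of a living patient who was never contacted. Two results are at stake: the overall functional distribution, and the comparison between states if they differ in their share of severe survivors.

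**Working it through.** **No plan figure to reproduce.** The Protocol gives no mortality, disability or attendance rate, and section 7.2.1 gives n = 100 without inputs. All rates below are assumptions, and 100 is used only as a denominator. The Protocol does not define a favourable eGOS category; here it means survivors without severe disability.

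**Notation.** d = dead by 6 months; s = severely disabled survivors; f = 1 - d - s = true favourable share; g = clinic attendance of favourable survivors; a = clinic attendance of severely disabled survivors.

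**Formula, with every death scored in the eGOS death category:**

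observed favourable share = f·g / (f·g + s·a + d)

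**Main range:** s = 0.25, g = 0.90.

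| d | f (true) | a | Calculation | Observed | Bias (points) |
|---|---|---|---|---|---|
| 0.10 | 0.65 | 0.40 | 0.585 / (0.585 + 0.100 + 0.100) | 74.5% | +9.5 |
| 0.10 | 0.65 | 0.80 | 0.585 / (0.585 + 0.200 + 0.100) | 66.1% | +1.1 |
| 0.30 | 0.45 | 0.40 | 0.405 / (0.405 + 0.100 + 0.300) | 50.3% | +5.3 |
| 0.30 | 0.45 | 0.80 | 0.405 / (0.405 + 0.200 + 0.300) | 44.8% | -0.2 |

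**Sign of the bias.** The observed share exceeds f only when g > (d + s·a) / (d + s), because deaths are fully ascertained and offset some of the loss of disabled survivors. In the last row the threshold is (0.30 + 0.20) / 0.55 = 0.909, just above g = 0.90. So a modest attendance gap need not push the result upward.

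**A second set of assumptions:** d = 10-30%, s = 10-20%, 0-50% of severe survivors absent, 0-10% of favourable survivors absent. With deaths scored, the bias runs from -2.6 to +7.8 points. Two cases, both with d = 20%, s = 20%, f = 60%:
- Half the severe survivors absent, all favourable present: 60 / (60 + 10 + 20) = 66.7%, or +6.7 points.
- All severe survivors present, 10% of favourable absent: 54 / (54 + 20 + 20) = 57.4%, or -2.6 points.

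**Comparison between states.** Take two states with the same true favourable share of 55%, g = 0.90, a = 0.50, deaths scored.
- State A, 10% dead and 35% severe: 0.495 / (0.495 + 0.175 + 0.100) = 64.3%.
- State B, 30% dead and 15% severe: 0.495 / (0.495 + 0.075 + 0.300) = 56.9%.

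The false gap is 64.3 - 56.9 = 7.4 points. It arises from the different mix alone, with identical attendance behaviour in both states.

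**Living non-attenders per 100 in the main range:** 0.10·f·100 = 4.5 to 6.5 favourable, plus 25·(1 - a) = 5 to 15 disabled, so about 10 to 22 patients.

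**The case against.** **Silence is not prohibition.** The Protocol does not rule out another route. The 6-month interview in Appendix 2 has no fixed mode, a carer could answer at the visit, and section 8.4 describes a multidisciplinary neurotrauma clinic with neurorehabilitation and neuropsychology, which suits disabled survivors. All patients are offered the appointment. This stands in part: loss of disabled patients is plausible but not documented, and it cannot be said that they are unable to attend. But an offer does not secure a score, and all three descriptions of the assessment name only the clinic.

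**The direction is built into the assumptions.** Lower attendance by disabled survivors is assumed, and patients who recover well may also stay away. This stands. It is why the range reaches zero and can be slightly negative.

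**The stronger reading: deaths drop out.** A reader might infer that patients who died also disappear from the results. On the main assumptions, removing d from the denominator gives an overstatement between 0.585 / 0.785 - 0.65 = +9.5 points and 0.405 / 0.505 - 0.45 = +35.2 points. The documents do not support this. Nothing restricts eGOS to attenders, eGOS has a death category that needs no appointment, and the scoring of deaths may be set out in a statistical analysis plan that is not at hand. The 10-35 point figure is therefore not a finding against this Protocol.

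**SF-36 is undefined after death by any route.** Correct. How to report it in the presence of deaths is an analysis matter. The collection rule adds only the loss of living non-attenders.

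**Conclusion.** The point holds as a limited gap in data collection. The Protocol states one route for the 6-month eGOS and SF-36 and none for living patients who do not attend. With deaths scored, the assumed rates put the bias in the favourable share at about 0 to +10 points; the second set of assumptions gives about -3 to +8. A false gap of about 7 points between two equally good states is possible under the illustrated mix. An upward bias requires severely disabled survivors to be missed sufficiently more often than favourable ones, which is likely in kind but cannot be quantified from the documents.

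Only a secondary objective is affected. The change is still worth making, because a 6-month score not obtained at the time cannot be recovered by analysis.

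**What to change.** Amend the Study Flow Chart, section 3 and section 5, and align the 6-month row of Appendix 2, to state that:

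1. eGOS is obtained for every enrolled patient, not only for clinic attenders.
2. Vital status at 6 months is taken from records, and deaths are entered in the eGOS death category.
3. For living patients who do not attend, the existing research team completes eGOS, and SF-36 where possible, by telephone, post or carer interview.
4. The mode of administration and the respondent are recorded.
5. SF-36 is reported among assessed survivors, with the numbers dead and missing shown for each pathological state.

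The cost is small: on the assumed rates, about 10 to 22 extra contacts per 100 patients, spread over the five-year study period. The downside is mixed modes of administration, which may add some measurement variation. Recording the mode lets this be examined.
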